6.3.1 Study Treatment

Regorafenib is administered as monotherapy during the study once daily for 3 of every 4 week cycle. The dose of Regorafenib is 120 mg once daily for the first cycle, which will be escalated to 160 mg once daily from the second cycle if no Regorafenib-associated toxicities greater than grade 1 occur during the first cycle.

Three 40-mg Regorafenib tablets (with potential escalation to 4 tablets or reduction to 2 tablets) should be taken once a day with approximately 8 fluid ounces (240 mL) of water after a low-fat (<30% fat) meal. Some examples of low fat meals are:

- Two slices of white toast with 1 tablespoon of low-fat margarine and 1 tablespoon of jelly and 8 ounces (240 mL) of skim milk (approximately 319 calories and 8.2 g of fat).
- One cup of cereal (i.e. Special K), 8 ounces (240 mL) of skim milk, one piece of toast with jam (no butter or marmalade), apple juice, and one cup of coffee or tea (2 g fat, 17 g protein, 93 g of carbohydrate, 520 calories).

6.3.1.1 Dose Reduction and escalation Levels

The starting dose of Regorafenib is 120 mg once daily. The dose will be escalated to 160 mg once daily from the second cycle if no Regorafenib-associated toxicities greater than grade 1 occur during the first cycle.

Study medication will be administered on a 3 weeks on/1 week off schedule [3 weeks out of every 4].

Doses will be delayed or reduced for clinically significant hematologic and non-hematologic toxicities that are related to protocol therapy according to the guidelines shown in the Dose Delays/Dose Modifications table that follows. Dose modifications will follow predefined dose levels. Dose adjustments for hematologic toxicity are based on the blood counts obtained in preparation for the day of treatment.

The modifications of Regorafenib will follow the following predefined dose levels:

Dose level +1	160 mg po qd	Four 40-mg tablets of Regorafenib
Dose level 0 (standard starting dose)	120 mg po qd	Three 40-mg tablets of Regorafenib
Dose level - 1	80 mg po qd	Two 40-mg tablets of Regorafenib

If a subject experiences more than one toxicity, dose reduction should be according to the toxicity with the highest grade

In the case of two or more toxicities of the same grade, the investigator may dose reduce according to that deemed most causally related to study treatment

If a dose reduction has been performed, intra-subject dose re-escalation can be considered (up to the maximal 160 mg daily dose) at the discretion of the treating physician provided that the toxicity(ies) has resolved to baseline.

The following tables outline dose adjustments for toxicities related to study drug except hand-foot skin reaction, hypertension and liver function test abnormalities.

Table 6-1: Recommended dose modification for toxicities except hand-foot-skin reaction, hypertension and ALT/ST/bilirubin

NCI-CTCAE v4.0 ^a	Dose Interruption	Dose Modification ^b	Dose for Subsequent Cycles
Grade 0-2	Treat on time	No change	No change
Grade 3	Delay until ≤ Grade 2 ^c	Reduce by 1 dose level	If toxicity remains < Grade 2, dose re-escalation can be considered at the discretion of the treating investigator. If dose is re-escalated and toxicity (≥ Grade 3) recurs, institute permanent dose reduction.
Grade 4	Delay until ≤ Grade 2 ^c	Reduce by 1 dose level. Permanent discontinuation can be considered at treating investigator's discretion.	

a. NCI-CTCAE = National Cancer Institute - Common Terminology Criteria for Adverse Events, version 4.0

b. Excludes alopecia, non-refractory nausea/vomiting, non-refractory hypersensitivity and nonclinical and asymptomatic laboratory abnormalities.

c. If no recovery after a 4 week delay*, treatment should be permanently discontinued unless subject is deriving clinical benefit.

The table above outlines dose adjustments for hematologic and non-hematologic toxicities related to Regorafenib except HFSR and hypertension.

In addition to these recommended dose modifications, subjects who develop diarrhea, mucositis, anorexia or other events predisposing to fluid loss or inadequate fluid intake should be carefully monitored and rehydrated as clinically necessary. This is in order to minimize the risk of postural hypotension and renal failure.

Table 6-2: Grading for Hand-Foot-Skin-Reaction

	Grade 1	Grade 2	Grade 3
NCI-CTCAE v4.0 Palmar-plantar erythrodysesthesia syndrome	Minimal skin changes or dermatitis (e.g., erythema, edema, or hyperkeratosis) without pain	Skin changes (e.g., peeling, blisters, bleeding, edema, or hyperkeratosis) with pain	Severe skin changes (e.g., peeling, blisters, bleeding, edema, or hyperkeratosis) with pain
Further description / examples of skin changes	Numbness, dysesthesia / paresthesia tingling, painless swelling, or erythema of the hands and/or feet	Painful erythema and swelling of the hands and/or feet	Moist desquamation, ulceration, blistering, or severe pain of the hands and/or feet
Effect on activities	Does not disrupt normal activities	Limiting instrumental activities of daily life (e.g., preparing meals, shopping for groceries or clothes, using the telephone, managing money)	Limiting self-care activities of daily life (e.g., bathing, dressing and undressing, feeding self, using the toilet, taking medications) and not bedridden
a. Palmer-plantar erythrodysesthesia syndrome is a disorder characterized by redness, marked discomfort, swelling, and tingling in the palms of hands or the soles of the feet.			

Table 6.3 Recommended dose modification for hand-foot-skin reaction^a

Grade of event (NCI-CTCAE v4.0)	Occurrence	Suggested Dose Modification
Grade 1	Any	Maintain dose level and immediately institute supportive measures for symptomatic relief
Grade 2	1 st occurrence	Consider decreasing dose by one dose level and immediately institute supportive measures. If no improvement, interrupt therapy for a minimum of 7 days, until toxicity resolves to Grade 0-1 ^{b, c}
	No improvement within 7 days or 2 nd occurrence	Interrupt therapy until toxicity resolves to Grade 0-1. ^c
	3 rd occurrence	When resuming treatment, treat at reduced dose level ^b
	4 th occurrence	Interrupt therapy until toxicity resolves to Grade 0-1. ^c When resuming treatment, decrease dose by one dose level. ^{b, d} Discontinue therapy
Grade 3	1 st occurrence	Institute supportive measures immediately. Interrupt therapy for a minimum of 7 days until toxicity resolves to Grade 0-1. ^c When resuming treatment, decrease dose by one dose level. ^{b, d}
	2 nd occurrence	Institute supportive measures immediately. Interrupt therapy for a minimum of 7 days until toxicity resolves to Grade 0-1. ^c When resuming treatment, decrease dose by one additional dose level ^{b, d}
	3 rd occurrence	Discontinue treatment permanently.

a. More conservative management is allowed if judged medically appropriate by the investigator.
b. If toxicity returns to Grade 0-1 after dose reduction, dose re-escalation is permitted at the discretion of the investigator if subject has completed one cycle at reduced dose without recurrence of event.
c. If there is no recovery after a 4-week delay, treatment with Regorafenib will be discontinued permanently.
d. Subjects requiring dose reductions below 80 mg daily should go off protocol therapy.
e. The maximum daily dose is 160 mg.

(For studies with combination therapy, consider including the following statement "The other study treatment may be continued").

At first occurrence of HFSR, independent of grade, prompt institution of supportive measures such as topical emollients, low potency steroids, or urea-containing creams should be administered.

Recommended prevention/management strategies for skin toxicities consistent with HFSR are summarized below:

Control of calluses

Before initiating treatment with Regorafenib:

- Check condition of hands and feet.
- Suggest a manicure/pedicure, when indicated.

- Recommend pumice stone use for callus or 'rough spot' removal.

During Regorafenib treatment:

- Avoid pressure points.
- Avoid items that rub, pinch or create friction.

Use of creams

- Non-urea based creams may be applied liberally.
- Keratolytic creams (e.g. urea-based creams, salicylic acid 6%) may be used sparingly and only to affected (hyperkeratotic) areas.
- Alpha hydroxyl acids (AHA) based creams may be applied liberally 2 times a day. Approximately 5% to 8% provides gentle chemical exfoliation.
- Topical analgesics (e.g. lidocaine 2%) are to be considered for pain control.
- Topical corticosteroids like clobetasol 0.05% should be considered for subjects with Grade 2 or 3 HFSR. Avoid systemic steroids.

Tender areas should be protected as follows:

- Use socks/gloves to cover moisturizing creams
- Wear well-padded footwear
- Use insole cushions or inserts (e.g. silicon, gel)
- Foot soaks with tepid water and Epson salts

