However, when starting at the US FDA approved dose of 160 mg once daily for colon cancer and GIST, Regorafenib dose reductions owing to toxicities are common and may be necessary in up to 60-70% of patients (57). The most common adverse events (AEs) of any grade that occurred in $\geq 10\%$ of patients include fatigue, decreased appetite and food intake, hand-foot skin reaction (HFSR), also known as palmar-plantar erythrodysesthesia or PPE, diarrhea, mucositis, weight loss, infection, and hypertension. Interestingly, most AEs occurred early in the treatment course, during cycles 1 and 2, and their incidence decreased over subsequent cycles of therapy. Further, the dosing of Regorafenib remained relatively stable after three cycles of treatment, and there was no evidence of cumulative toxicity. These data suggest that the incidence of drug-related AEs decreases over time, and that proactive AE management early on may help to decrease the incidence or severity of those AEs that occur during the course of treatment, thus enabling better treatment compliance and adherence to therapy (58). Therefore, a robust rationale may be made to start at a dose of 120 mg once daily for 3 of every 4 weeks and incorporate close monitoring in the initial 2 cycles followed by gradual tapering of monitoring. In addition, the accrual of performance status 0-1 patients only (and excluding PS=2 patients) will mitigate the risk of AEs.

We propose a non-randomized proof-of-concept phase II trial to evaluate Regorafenib for patients with metastatic progressive urothelial carcinoma following 1-3 prior chemotherapy regimens who still have an ECOG performance status 0-1. Given the lack of validated predictive biomarkers for the efficacy of Regorafenib, all patients will be enrolled. Additionally, the initial dose will be 120 mg daily since Regorafenib dose reductions are common in colorectal cancer and GIST patients (see data below). However, dose will be escalated to 160 mg daily from cycle 2 day 1 or later if no Regorafenib-related >grade 1 toxicities are seen in cycle 1. Moreover, close monitoring is incorporated especially during the first 2 cycles, which then gradually tapers (see schedule table below). However, given a disease with substantial unmet needs and the lack of any FDA approved salvage agents for this disease, the potential benefits provided by this strategy are expected to outweigh the risks.

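### The re-escalation clause in section 6.3.1.1 caps at 160 mg without reference to the cycle 1 toxicity condition, so under Table 6-1 a Grade 3 event can lead to 160 mg when a Grade 2 event cannot

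*Combined protocol and SAP*

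**What the plan says.** **Escalation condition.** Section 6.3.1 starts every patient at 120 mg, "escalated to 160 mg once daily from the second cycle if no Regorafenib-associated toxicities greater than grade 1 occur during the first cycle". Section 6.3.1.1 repeats the condition: "if no Regorafenib-associated toxicities greater than grade 1 occur during the first cycle". Section 4 sets the same toxicity threshold, and section 1.2 ties escalation to cycle 1 and presents the lower starting dose as a response to the frequent dose reductions seen with this drug.

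**Re-escalation clause.** Further down section 6.3.1.1, the trigger is a reduction: "If a dose reduction has been performed, intra-subject dose re-escalation can be considered". The ceiling and the decision-maker follow: "intra-subject dose re-escalation can be considered (up to the maximal 160 mg daily dose) at the discretion of the treating physician". The toxicity must have resolved to baseline.

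**Dose levels and tables.** The levels are +1 (160 mg), 0 (120 mg, the start) and -1 (80 mg). Table 6-1 makes no modification at Grades 0 to 2 and reduces by one level at Grade 3 or 4. After Grade 3 it allows re-escalation and states no ceiling of its own. Table 6.3, for hand-foot skin reaction (HFSR), allows re-escalation after a reduction (footnote b) and adds in footnote e: "The maximum daily dose is 160 mg".

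**The concern.** The escalation condition is worded as a rule and the re-escalation clause as a discretion, and both end at 160 mg. Nothing says which prevails for a patient who failed the first and then falls under the second. If the clause is followed as written, a patient who did worse in cycle 1 can have access to a dose that is closed to one who did better. That dose is also above the one at which the severe event occurred.

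The starting dose with conditional escalation is part of the protocol's stated approach to tolerability. If sites can reach 160 mg by a second route, the condition does not do what sections 1.2 and 6.3.1 say it does. Two sites could then treat identical patients differently while both comply with the protocol.

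**Working it through.** The plan gives no figure for this point and no arithmetic applies. The check traces each toxicity table literally for a patient on 120 mg in cycle 1 and asks three things. Is the cycle 1 condition met? Does the table provide for a reduction? If so, does the re-escalation clause then apply, with its 160 mg ceiling?

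| Related event in cycle 1 at 120 mg | Cycle 1 condition met? | Reduction under the table? | 160 mg reachable on the literal text? |
|---|---|---|---|
| Table 6-1, Grade 1 | Yes | No | Yes, by planned escalation |
| Table 6-1, Grade 2 | No | No | No; the clause is not triggered |
| Table 6-1, Grade 3 | No | Yes, to 80 mg | Yes, by the clause |
| Table 6-1, Grade 4 | No | Yes, unless treatment is stopped | Yes, by the clause, if treatment continues |
| HFSR, Grade 2 (Table 6.3) | No | May be considered at first occurrence | Yes, if reduced |
| HFSR, Grade 3 (Table 6.3) | No | Yes | Yes |
| Hypertension, Grade 2 (Table 6-4) | No | No | No |
| Hypertension, Grade 3 (Table 6-4) | No | Only if blood pressure stays uncontrolled | Only if reduced |
| AST/ALT, Grade 2 (Table 6.5) | No | No | No |
| AST/ALT, Grade 3 (Table 6.5) | No | Yes, if treatment is restarted | Yes, by the general clause |

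The inversion is clearest in the second and third rows, which fall under one table and one clause:

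1. Grade 2 diarrhea at 120 mg: the condition fails, Table 6-1 leaves the dose alone, no reduction has taken place, and the clause cannot apply. The patient stays at 120 mg.
2. Grade 3 diarrhea at 120 mg: the condition fails, Table 6-1 reduces to 80 mg, and the event resolves to baseline. The clause now applies, and its only ceiling is 160 mg.

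The HFSR rows limit the claim. A Grade 2 reaction may itself be reduced, and footnote b then permits re-escalation, so Grade 2 and Grade 3 patients both have a route. The cycle 1 condition is still bypassed for HFSR, but severity is not inverted.

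I found no passage that ranks the condition against the clause, or that limits re-escalation to a dose already held.

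**The case against.** The strongest reply is linguistic. Re-escalation ordinarily means going back towards a dose already taken, and the 160 mg in brackets fits a patient who met the cycle 1 condition, reached 160 mg and was later reduced. The condition opens the same section and is nowhere set aside. This is a reasonable reading and may be the intended one. But the clause covers a patient with any reduction, and the only ceiling it names is 160 mg. Footnote e is equally unqualified.

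There are also safeguards. Re-escalation is discretionary and needs recovery to baseline. Table 6-1 makes the reduction permanent if Grade 3 or worse toxicity recurs after re-escalation. HFSR needs a full cycle at the lower dose without recurrence. These limit when the dose may rise and what follows a recurrence; they do not settle how high it may go.

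Four stronger readings are tempting, and the documents do not support them:

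- **That moderate toxicity is always barred and severe toxicity always admitted.** HFSR contradicts the first half. Hypertension at Grade 3 with control regained restarts at the same level, and Grade 4 hypertension and the highest transaminase elevations lead to discontinuation.
- **That the tables forbid the planned escalation at low grades.** Table 6.3 says of Grade 1 HFSR "Maintain dose level and immediately institute supportive measures for symptomatic relief", and Table 6-1 leaves the dose unchanged for later cycles at Grades 0 to 2. But the Table 6-1 row includes Grade 0. Taken literally it would bar every escalation, so it most sensibly means no change driven by toxicity. Table 6.3 offers suggestions, and Tables 6-4 and 6.5 do not tell sites to hold the level at low grades. This merits at most an optional clarification.
- **That the start of escalation is inconsistent.** Section 1.2 has "escalated to 160 mg daily from cycle 2 day 1 or later" and sections 4 and 6.3.1 say from the second cycle. These are compatible.
- **That the cited rates give the number of patients affected.** The 43.8% in section 1.3.2 mixes interruptions with reductions and does not isolate patients who started at 120 mg. The 17% for Grade 3 or worse HFSR comes from a trial dosed at 160 mg. Neither counts patients reduced from 120 mg who recover and are then considered for 160 mg.

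**Conclusion.** The point holds in a limited form. The cycle 1 condition and the re-escalation ceiling disagree about who may receive 160 mg, and nothing else in the protocol resolves it. For Table 6-1 toxicities the literal result is inverted: Grade 3 at 120 mg has a route to 160 mg and Grade 2 has none. For HFSR the condition can be bypassed without that inversion. For Grade 3 hypertension the route exists only where a reduction is made.

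The conclusion assumes that the clause is read as worded, covering any patient with a reduction up to 160 mg. If re-escalation means only a return to a dose previously held, the conflict disappears, but the protocol would have to say so. The number of patients affected cannot be estimated from the documents.

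A reader might infer that the primary analysis is compromised. The documents do not show that: the PFS6 threshold, the decision rule of five or more progression-free patients and the stated power do not depend on this rule. What is affected is patient safety and the clarity of the dosing strategy being tested. That makes it a wording error that should be corrected, and more than a missing detail.

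**What to change.** Reconcile sections 6.3.1 and 6.3.1.1 and the footnotes to Table 6.3 so that the cycle 1 condition and the re-escalation ceiling agree. Specifically, state whether the 160 mg ceiling applies to patients who did not meet the cycle 1 condition or who never held 160 mg, and word the clause and footnote e to match. Check sections 1.2 and 4 against the result. Which rule prevails is the sponsor's decision; none is proposed here.

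Optional: add a sentence saying that the no-change entry in Table 6-1 and the Grade 1 entry in Table 6.3 concern toxicity-driven changes only, or otherwise how they rank against the planned escalation at cycle 2.

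The cost is an amendment to the wording and a clarification to sites, with no new assessments. The downside is slightly less investigator discretion on dose.

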Regorafenib is a UGT1A1 inhibitor. Mild, indirect (unconjugated) hyperbilirubinemia may occur in patients with Gilbert's syndrome.

Table 6.5: Dose Modification/interruption for alanine aminotransferase and/or aspartate aminotransferase increases related to study drug

Increases in ASL/ALT (per NCI-CTCAE v 4.0)	1st Occurrence	Restart	Recurrence
AST and/or ALT < 5 X ULN (<Grade 3)	Continue dosing, with weekly monitoring of liver function until transaminases return to < 3 X ULN (< Grade 1) or baseline.		
ALT and/or AST > 5 X ULN (> Grade 3)	Interrupt dosing, with weekly monitoring until transaminases return to < 3 X ULN or baseline.	If the potential benefit of reinitiating Regorafenib is considered to outweigh the risk of hepatotoxicity: reduce 1 dose level and measure serum transaminases weekly for at least 4 weeks.	Discontinue
ALT and/or AST > 20 X ULN (> Grade 4)	Discontinue		
ALT and/or AST > 3 X ULN (> Grade 2) with concurrent bilirubin > 2 X ULN	Discontinue treatment and measure serum transaminases weekly until resolution. Exception: subjects with Gilbert's syndrome who develop elevated transaminases should be managed as per the recommendations outlined above for ALT/AST elevations.		

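### For regorafenib-related grade 3–4 bilirubin with ALT/AST not above 3 × ULN, the dose-modification scope statements disagree and no hold or restart rule clearly governs

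*Combined protocol and SAP*

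**What the plan says.** Three statements in Section 6.3.1.1 set the scope of Table 6-1.

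- The lead-in covers drug-related toxicities "except hand-foot skin reaction, hypertension and liver function test abnormalities".
- The table's title makes the same kind of exclusion and names bilirubin alongside the transaminases.
- The sentence after the footnotes reads: "The table above outlines dose adjustments for hematologic and non-hematologic toxicities related to Regorafenib except HFSR and hypertension". It does not except liver tests.

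In Table 6-1, the grade 3 and grade 4 rows both say "Delay until ≤ Grade 2", followed by a reduction of one dose level. At grade 4, permanent discontinuation may be considered. Footnote b, attached to the dose-modification column, exempts asymptomatic laboratory abnormalities. Footnote c, attached to the delay column, sets a four-week limit unless the patient is benefiting.

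The Liver Function Abnormalities text sends regorafenib-related worsening of serum liver tests to Table 6-5. That table is titled for ALT and/or AST increases. Its first row applies below 5 × ULN and says: "Continue dosing, with weekly monitoring of liver function until transaminases return to < 3 X ULN". Its only bilirubin condition is in the fourth row, "ALT and/or AST > 3 X ULN (> Grade 2) with concurrent bilirubin > 2 X ULN", where the action is to discontinue, with an exception for Gilbert's syndrome.

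**The concern.** Hyperbilirubinemia is a known toxicity of this drug. Section 1.3.2 lists it among the most frequent grade 3+ events in the colorectal trial, and the text above Table 6-5 describes regorafenib as a UGT1A1 inhibitor. Section 7.1, note C, requires bilirubin weekly in the first two cycles, so the trial will generate these values.

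If bilirubin reaches grade 3 or 4 while ALT/AST are normal or only slightly raised, a site needs to know whether to hold, when to restart and at what dose. Different sentences point to different answers, and the table that the protocol names for liver tests leans toward continued exposure. At stake are patient safety and uniform dosing across sites.

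**Working it through.** No figure in the plan needs reproducing; the check is a trace of the written rules.

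**Is bilirubin a liver test in this protocol?** Yes. Section 7.1, note H, and the clinical laboratory table in Section 7.4.1.3 both list total bilirubin among the liver function tests. The Liver Function Abnormalities text therefore takes in a drug-related bilirubin rise.

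**Case 1: ALT/AST raised but not above 3 × ULN, with grade 3–4 bilirubin.** Take ALT 2.9 × ULN and bilirubin 5 × ULN to illustrate the row logic. The bilirubin grade cut-points are in the CTCAE, not printed in the protocol.

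| Table 6-5 row | Condition | Met? |
|---|---|---|
| 1 | ALT/AST below 5 × ULN | Yes, 2.9 < 5 |
| 2 | above 5 × ULN | No |
| 3 | above 20 × ULN | No |
| 4 | above 3 × ULN and bilirubin above 2 × ULN | No, 2.9 < 3, although 5 > 2 |

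Only row 1 matches, and its action is to continue with weekly monitoring. The row does not mention bilirubin.

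**Case 2: normal ALT/AST, with grade 3–4 bilirubin.** Table 6-5 is titled for transaminase increases, so no row applies.

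**The same patients under Table 6-1.** By the title and lead-in, bilirubin is excluded and the table gives no action. By the sentence after the table, bilirubin is included and dosing is delayed to grade 2 or lower. Footnote b could lift the dose reduction for an asymptomatic finding but not the delay, because it is attached to the modification column.

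The written result is therefore continue, no row, or delay, depending on the sentence followed and whether ALT/AST are raised.

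**Size.** Section 1.3.2 gives 8% grade 3+ hyperbilirubinemia at 160 mg in colorectal cancer. If that rate carried over to 35 patients, 35 × 0.08 = 2.8 would have the event. The share that is drug-related with ALT/AST at or below 3 × ULN is not given. Assuming it lies anywhere from 0 to 1, the expected number is 0 × 2.8 = 0 to 1 × 2.8 = 2.8. No rate is given for the 120 mg starting dose. This is a bracket under an assumption, not an estimate.

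**The case against.** The strongest reply is that this is one careless summary sentence. The Table 6-1 title, its lead-in and the Liver Function Abnormalities text all agree that liver tests are handled elsewhere, so the sentence after Table 6-1 is the outlier. That stands. But correcting the sentence alone would remove the clash and still leave high bilirubin with ALT/AST at or below 3 × ULN without a hold or restart rule.

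A reader might infer that the protocol instructs sites to continue dosing at any bilirubin level, or that two equal rules order opposite actions. The documents do not support either. Row 1 manages a transaminase rise and is silent on bilirubin; silence is not permission. One stray sentence against three consistent statements is not a rival rule of equal standing. Nor does the contrast between ALT just below and just above 3 × ULN prove much, since any threshold creates a step.

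There are real backstops. Section 6.3.1.1 states: "Doses will be delayed or reduced for clinically significant hematologic and non-hematologic toxicities that are related to protocol therapy". It also states: "If a subject experiences more than one toxicity, dose reduction should be according to the toxicity with the highest grade". Section 5.2.1 requires withdrawal if the investigator thinks continuing would be harmful. Section 9.2 makes the principal investigator the contact for dose questions. Section 7.4.1.4.1 provides weekly committee review of adverse reactions and a monthly cross-site teleconference. Entry bilirubin is capped at 1.5 × ULN, and any related cycle 1 toxicity above grade 1 blocks escalation.

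These limit the harm, and many investigators would probably hold the drug. They do not supply the rule. The general statement works through a table whose title leaves bilirubin out, the highest-grade rule concerns dose reduction and does not say which table covers bilirubin, and the others rest on case-by-case judgement.

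**Conclusion.** The point holds as an inconsistency of scope together with a gap. For regorafenib-related grade 3–4 bilirubin with ALT/AST not above 3 × ULN, the protocol does not clearly say whether to hold, when to restart or at what dose. This rests on the current wording of Section 6.3.1.1 and Table 6-5 and on bilirubin being a liver test in this protocol.

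The severity is minor. The number affected cannot be estimated from the documents, and judgement would probably lead many sites to hold the drug. A reader might also infer a threat to the primary result. The documents give no basis for that: the sample size, the exact binomial test and the decision rule for PFS6 are untouched.

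**What to change.** 1. Use one exception phrase in the Table 6-1 title, its lead-in and the sentence after the table: *except HFSR, hypertension and ALT/AST elevations (Table 6-5)*.

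2. Under Table 6-5 add: *Regorafenib-related Grade 3 or 4 bilirubin elevation that does not meet row 4 follows Table 6-1 (delay until ≤ Grade 2, footnotes b and c as written), in addition to the applicable ALT/AST row; the stricter action applies. Mild indirect hyperbilirubinemia in Gilbert's syndrome needs no dose change.*

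Leave the row 1 trigger, and row 4 with its Gilbert's exception, unchanged. Adding a bilirubin limit to row 1 would be a mistake: a Gilbert's patient with ALT 4 × ULN and grade 3 bilirubin, excepted from row 4, would then fall in no row of Table 6-5. With row 1 unchanged that patient keeps a transaminase rule.

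Whether to require dose reduction for asymptomatic bilirubin, by disapplying footnote b, would be a new clinical rule and is for the sponsor to decide.

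The cost is amendment wording only. No extra bilirubin sampling is needed in cycles 1–2, where it is already weekly; fractionation might be wanted in a patient with Gilbert's syndrome. The downside is an occasional dose hold for isolated bilirubin elevation.
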